### 3.3.2 Biomechanical Improvements

Significant reductions were observed, indicating improved movement quality.

**Table 4: Biomechanical Outcomes**

Measure	Baseline Mean ±pm SD	Week 6 Mean ±pm SD	Mean Change	Cohen's d	p-value
Knee Valgus Angle (deg)	12.52±pm2.72	10.28±pm2.53	-2.24	-3.91	<0.001
Spinal Curvature (deg)	4.98±pm1.54	4.27±pm1.40	-0.71	-2.97	<0.001

The 17.9% reduction in knee valgus angle and 14.3% reduction in spinal curvature demonstrate the BPIT protocol's effectiveness in improving joint mechanics and reducing injury risk factors.

[figure not shown]

Figure 3: Changes in knee valgus angle and spinal curvature from baseline to Week 6. Individual participant data are shown as gray lines, with mean  $\pm$  SD represented by black error bars.

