# 2. METHODS

## 2.2 Participants

Twenty-three healthy adults were enrolled.

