## 2.5 Outcome Measures

- **Primary:** Change in 1RM (squat, bench press, deadlift); Incidence of training-related injuries.
- **Secondary:** Change in HRV (RMSSD); Change in HRR; Change in EMG (rectus abdominis, quadriceps); Change in knee valgus angle and spinal curvature.

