#### 3.2.2 Injury Incidence

Only one mild muscle strain was reported, resulting in an injury incidence rate of 4.3% (1/23 participants) and an injury rate of 2.54 per 1000 training hours.

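### Protocol section 3.3.2 concludes that the falls in knee valgus and spinal curvature show BPIT to be effective on joint mechanics and injury risk factors; the documents reviewed support only an uncontrolled mean change in each angle.

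*Protocol*

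**What the plan says.** Protocol section 3.3.2 opens with "Significant reductions were observed, indicating improved movement quality". After Table 4, the report says that the percentage falls in the two angles demonstrate BPIT's "effectiveness in improving joint mechanics and reducing injury risk factors". The Executive Summary lists the valgus result under better biomechanical efficiency, and the Conclusions (section 5) claim strong evidence that BPIT lowers injury risk.

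The planned question was narrower. Protocol section 1.3 asks about the impact on joint biomechanics. Section 2.5 lists "Change in knee valgus angle and spinal curvature" as a secondary outcome, and SAP section 1 says the same, in degrees. SAP section 5 analyses these endpoints by a before-after test, with Cohen's d and a 95% CI. SAP section 4 handles injury separately, as a proportion and a rate.

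On the population and the injury data, the Protocol says "Twenty-three healthy adults were enrolled" (section 2.2) and "Only one mild muscle strain was reported" (section 3.2.2). Section 4.6 acknowledges that the study had one arm and no control group.

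**The concern.** Three steps separate a fall in an angle from the stated conclusion: that a smaller angle is better in these people, that the angle is a risk factor for injury, and that BPIT caused the fall. The documents reviewed supply none of the three.

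This matters because injury reduction is half of the primary objective and the direct injury data amount to one event. The sentence under Table 4 gives the injury message a second support that uses no injury data. Correcting the reading of the injury incidence alone would leave that support in place. A reader of the Conclusions could then believe that biomechanical evidence corroborates injury prevention, when no such link was tested.

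**Working it through.** **1. The report's own figures.** Inputs are from Table 4.
- Valgus: 12.52 to 10.28, change -2.24; 2.24 / 12.52 = 17.9%.
- Curvature: 4.98 to 4.27, change -0.71; 0.71 / 4.98 = 14.3%.

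Both stated percentages reproduce. The arithmetic is not in dispute.

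**2. The confidence intervals that the SAP plans but Table 4 does not show.** Assume that Cohen's d is the paired version named in SAP section 3, so that SD of change = change / d, with n = 23, √23 = 4.796 and a t quantile on 22 df of 2.074.

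| | Valgus | Curvature |
|---|---|---|
| SD of change | 2.24 / 3.91 = 0.573 | 0.71 / 2.97 = 0.239 |
| Standard error | 0.573 / 4.796 = 0.1195 | 0.239 / 4.796 = 0.0498 |
| Half-width | 2.074 × 0.1195 = 0.248 | 2.074 × 0.0498 = 0.103 |
| 95% CI for change (degrees) | -2.49 to -1.99 | -0.81 to -0.61 |
| t = d × √n | -3.91 × 4.796 = -18.8 | -2.97 × 4.796 = -14.2 |
| Change / baseline SD | -2.24 / 2.72 = -0.82 | -0.71 / 1.54 = -0.46 |

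The t values agree with the reported p < 0.001. A mean change between the two visits is therefore well supported on the reported figures. The large paired d reflects a small SD of change; against the baseline spread between people, the shifts are 0.82 and 0.46 SD. Neither measure says whether the change is beneficial or what caused it.

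**3. Each step of the inference against the documents.**
- *Smaller is better.* Protocol sections 1.3 and 2.5 and SAP section 1 give no direction, normal range, threshold or meaningful change for either angle. They do not say which spinal curvature was measured. The participants were healthy adults, and no selection for abnormal angles is described.
- *The angle is an injury risk factor.* No passage establishes this, and no source is cited at the sentence. SAP sections 4 and 5 plan no analysis that relates angle to injury.
- *BPIT caused the fall.* There is no control group (section 4.6), so learning, retest effects and regression to the mean are not excluded.

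**4. Could the study's own data supply the missing link to injury?** One of 23 participants was injured. In an exact rank comparison of 1 injured with 22 uninjured, the most extreme result has one-sided p = 1/23 = 0.043 and two-sided p = 2/23 = 0.087. No two-sided result below 0.05 is attainable. Nobody planned or reported this test; the figure shows only that the gap cannot be filled from within the study.

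**The case against.** The best defence has four parts.

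*Neutral wording is ordinary drafting.* The documents use change-in wording for nearly every continuous endpoint, including 1RM, HRV and EMG, and the Background says that BPIT aims to limit biomechanical stress. This stands to a degree: the absence of a direction proves little alone. A reader might infer that the beneficial direction was chosen after the result was seen. The documents do not support that. No passage shows it, and Appendix D refers to a separate protocol file, version 1.0, which was not among the documents reviewed and might state a direction. All that can be said is that none is stated in these documents.

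*The sentence speaks of risk factors, not injuries.* This is correct. A reader might take it as claiming an association between angle and injury within the study, but it reports none. The fair criticism is that risk-factor status is unsupported where it is asserted. Outside evidence might support it, and the reference list includes an evaluation of BPIT and injury prevention, but the sentence cites nothing. A study of 23 people could not be expected to validate such a surrogate.

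*The limitations are disclosed.* Section 4.6 concedes the lack of a control group, the small sample and the short duration. It does not mention the step from angle to injury risk, and the Conclusions are not tempered accordingly.

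*This is interpretive wording on secondary endpoints in a study that the SAP calls exploratory.* True, and it limits the weight of the point. The section title and the label of movement quality are loose language rather than extra endpoints; a change of title would be an editorial preference.

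**Conclusion.** The concern holds as a fault of inference. The reported data support mean falls of 2.24 degrees in valgus and 0.71 degrees in curvature over six weeks. They do not show that BPIT caused these falls, that smaller angles were better for these healthy adults, or that any injury risk factor was reduced. No reported number is wrong and no analysis changes, apart from showing the confidence intervals already planned.

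The conclusion rests on the documents supplied. If the separate protocol file or a citable source gives a direction, a threshold and evidence of risk-factor status, the second and third of these gaps could narrow. The missing control group would still rule out attributing the change to BPIT. The reconstructed intervals assume a paired Cohen's d and rounded inputs, and should be replaced by values from the participant data.

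**What to change.** Replace the concluding sentence under Table 4 with text such as:

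*Mean knee valgus angle fell by 2.24 degrees and mean spinal curvature by 0.71 degrees from baseline to Week 6 (95% CIs as planned in the SAP). Without a control group these changes cannot be attributed to BPIT, and the study did not assess whether they alter injury risk.*

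Then:
- delete the phrase on injury risk factors under Table 4 and the phrase on movement quality at the start of section 3.3.2;
- in the Executive Summary, report the valgus result as a change in angle;
- make sure that the injury-risk claim in the Conclusions does not rest on these angles;
- if a prespecified direction and its justification exist elsewhere, state and cite them.

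The section title can stay. The change needs no new data, only edited text and the confidence intervals that the SAP already calls for. The downside for the sponsor is a less favourable secondary conclusion.

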### 3.3.3 Muscle Activation (EMG)

Improvements suggest enhanced neuromuscular efficiency.

**Table 5: EMG Outcomes**

Muscle Group	Baseline Mean ±pm SD (% MVC)	Week 6 Mean ±pm SD (% MVC)	Mean Change	Cohen's d
Rectus Abdominis	63.93±pm6.01	75.05±pm7.78	+11.12	4.05
Quadriceps	71.42±pm5.63	83.66±pm6.14	+12.23	4.65

These improvements in muscle activation (17.4% for rectus abdominis, 17.1% for quadriceps) suggest enhanced neuromuscular efficiency and motor unit recruitment following the BPIT

intervention.

[figure not shown]

Figure 4: Changes in EMG amplitude for rectus abdominis and quadriceps from baseline to Week 6. Individual participant data are shown as gray lines, with mean  $\pm$  SD represented by black error bars.

## 4. DISCUSSION

The BPIT protocol is highly effective, demonstrating statistically significant and clinically meaningful improvements across all measured outcomes, with large effect sizes ( $d$  ranging from 2.97 to 4.76). The low injury incidence rate (4.3%) supports its safety profile. The intensity cycling likely optimizes the balance between training stress and recovery, leading to enhanced adaptation.

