### 4.6 Limitations

The study had a single-arm design without a control group, a relatively small sample size ( $n=23$ ), and a short duration (6 weeks). Future research should employ randomized controlled trial designs with larger, more diverse populations.

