## 3. Primary Efficacy Analysis

- Paired t-test (or Wilcoxon signed-rank test if normality violated) comparing baseline vs. Week 6 for each 1RM exercise
- Effect size: Cohen's d (paired)
- Summary: Mean  $\pm$  SD at baseline and Week 6, mean change, 95% CI, p-value, Cohen's d

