#### **5. Secondary Efficacy Analyses**

All continuous secondary endpoints analysed exactly as primary (paired t-test/Wilcoxon, Cohen's d, 95% CI)

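### Section 4 calls the improvements clinically meaningful on every measured outcome, but neither supplied document states a criterion of meaningful change against which that could be judged

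*Protocol*

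**What the plan says.** Section 4 of the protocol document concludes that the programme is highly effective, "demonstrating statistically significant and clinically meaningful improvements across all measured outcomes". In the same sentence it cites large effect sizes, with d from 2.97 to 4.76.

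The outcomes are defined only as changes or as an incidence. Section 2.5 gives the primary outcomes as "Change in 1RM (squat, bench press, deadlift); Incidence of training-related injuries", and lists the secondary outcomes in the same form.

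SAP section 3 specifies a paired t-test or Wilcoxon test "comparing baseline vs. Week 6 for each 1RM exercise", with mean change, 95% CI, p-value and a paired Cohen's d. SAP section 5 carries this over: "All continuous secondary endpoints analysed exactly as primary". SAP section 4 gives injury an exact confidence interval for the proportion and a rate per 1,000 training hours.

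Section 4.6 begins "The study had a single-arm design without a control group" and adds the small sample and short duration. It does not qualify the claim of clinical meaning.

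**The concern.** The Discussion sentence makes two claims: that the changes are statistically significant, and that they matter clinically. The second needs a standard, such as a minimal important difference, a responder definition, a normal range or a measurement-error limit. No such standard appears in the objectives, the outcome definitions, the SAP or the results.

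The reader is left to take the effect sizes as the evidence, and values of d between 3 and 5 look overwhelming. If the metric does not measure importance, a main interpretive statement of the report has no basis, even though the tabulated mean changes are unaffected.

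The sentence also covers every measured outcome, and so includes injury incidence, a primary outcome on which no change was observed or could have been.

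**Working it through.** **1. Search for a criterion.** The continuous outcomes in Tables 2–5 number 3 (1RM) + 2 (resting heart rate, HRV) + 2 (knee valgus, spinal curvature) + 2 (EMG) = 9. Protocol sections 1.3 and 2.5 and SAP sections 1 and 3–5 give no threshold of meaningful change for any of them.

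**2. The stated range of d.** The smallest |d| in Tables 2–5 is 2.97 (spinal curvature) and the largest is 4.76 (HRV), so the range in section 4 matches the tables. The individual values cannot be recomputed, because the SD of the changes is not reported.

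**3. What that d measures.** The SAP specifies the paired form, d = mean change / SD of change. For spinal curvature the implied SD of change is 0.71 / 2.97 = 0.239 degrees. With n = 23:

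- t = 2.97 × √23 = 14.2 on 22 df
- implied 95% CI = 0.71 ± 2.074 × 0.239 / √23 = 0.61 to 0.81 degrees

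So a non-zero mean change follows from the reported d. Its importance does not. If the individual changes had been twice as variable (SD 0.478), d would be 0.71 / 0.478 = 1.49 for exactly the same 0.71 degrees.

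**4. The same changes in baseline SDs** (mean change / baseline SD):

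| Outcome | Change | Baseline SD | Reported d | Change / baseline SD |
|---|---|---|---|---|
| Squat (kg) | 22.91 | 22.49 | 3.44 | 1.02 |
| Bench press (kg) | 16.11 | 21.11 | 3.12 | 0.76 |
| Deadlift (kg) | 24.60 | 28.26 | 4.01 | 0.87 |
| Resting heart rate (bpm) | −6.02 | 9.20 | −4.01 | −0.65 |
| HRV RMSSD (ms) | 12.67 | 11.05 | 4.76 | 1.15 |
| Knee valgus (degrees) | −2.24 | 2.72 | −3.91 | −0.82 |
| Spinal curvature (degrees) | −0.71 | 1.54 | −2.97 | −0.46 |
| Rectus abdominis EMG (% MVC) | 11.12 | 6.01 | 4.05 | 1.85 |
| Quadriceps EMG (% MVC) | 12.23 | 5.63 | 4.65 | 2.17 |

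The range is 0.46 to 2.17, against 2.97 to 4.76 for paired d. Dividing instead by the root mean square of the baseline and Week 6 SDs gives 0.48 to 2.08. The order also shifts. Deadlift has a larger paired d than squat (4.01 against 3.44) but a smaller change in baseline SDs (0.87 against 1.02). None of these scales is a criterion of importance. The comparison shows only that a large paired d cannot stand in for one.

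**5. Injury.** Section 3.2.2 reports 1/23 = 4.3%. The Clopper-Pearson 95% CI is 0.1% to 21.9% (2.5% quantile of Beta(1, 23) and 97.5% quantile of Beta(2, 22)). There is no pre-study injury figure and no comparator, so no improvement can be calculated.

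**The case against.** The plan does more than test for zero change. SAP sections 3 and 5 call for mean changes with 95% CIs in native units, and section 4 for an exact CI and a rate for injury. A reader with an external standard could judge the changes from such estimates. Injury is itself a clinical primary endpoint with its own analysis. All of this stands, and it means the gap is narrow: there is estimation, but nothing to judge the estimates against. Tables 2–5 as supplied do not show the planned intervals, which makes the reader's own judgement harder.

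A reader might infer from "Twenty-three healthy adults were enrolled" that clinically meaningful change was impossible in this population. The documents do not support that. They give no normal ranges, so they show neither a deficit at baseline nor its absence. Section 3.3.2 presents the joint measures as risk factors for injury, and prevention can matter to healthy people. The point rests on the missing criterion alone.

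A reader might also infer that the changes are clinically trivial, or that a before-and-after design could never be read against a threshold. Neither follows. The 0.71 degrees is unassessed, not shown to be unimportant, and such a design can be set against an external threshold if one is stated.

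Appendix D names a separate protocol file, version 1.0, which was not among the documents supplied. A threshold in that file cannot be excluded. The supplied SAP says that its objectives come from the protocol, and it contains none.

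Finally, section 4.6 already concedes the lack of a control group, the small sample and the short duration. Those limits bear on attribution, precision and persistence. A control group would help attribute a change of 0.71 degrees to the programme, but would not show that it matters.

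**Conclusion.** The concern holds in this form: on the two documents supplied, the claim of clinical meaning has no stated basis for any of the nine continuous outcomes, and improvement on injury is undefined. The d values offered in support describe uniformity of change. In baseline SDs the same changes run from 0.46 to 2.17.

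This takes the reported means, SDs and d values at face value and reads d as the paired form that the SAP specifies. The t value and confidence interval for spinal curvature are back-calculated from the reported d. The finding is limited to the supplied documents. It does not say that the changes are unimportant, and it leaves the tabulated mean changes as they are.

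**What to change.** In section 4, delete the words 'and clinically meaningful' and limit the sentence to mean changes from baseline in the continuous outcomes reported in Tables 2–5. Deletion alone is not enough, because the sentence would still claim improvement on injury. Report injury separately as 1/23 with its exact 95% CI.

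Add to section 4.6: *No threshold of clinically meaningful change was pre-specified for any outcome, so clinical relevance was not assessed.*

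If the protocol file listed in Appendix D does contain pre-specified thresholds, cite them and report the results against them in place of that limitation. Any threshold chosen now would be chosen with the results known and must be labelled post hoc.

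The cost is a few sentences of text, with no new data, and a less favourable Discussion statement.

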## **EXECUTIVE SUMMARY**

This prospective, single-center, interventional study evaluated the efficacy of the **5-Line Principle of Balanced Intensity Training (BPIT)** in improving physical performance and reducing injury risk over a 6-week training period.

- **Participants:** Twenty-three participants (18 males aged 22-48 years, 5 females aged 20-33 years) completed the study with a mean adherence rate of 94.9%.
- **Key Findings:** The BPIT protocol demonstrated statistically significant improvements across all measured outcomes, including:
  - Strength gains of 15-25%.
  - Enhanced autonomic function (HRV increase of 12.67 ms).
  - Improved biomechanical efficiency (knee valgus reduction of 17.9%).
  - A low injury incidence rate of 4.3%.
- **Conclusion:** These findings support the BPIT method as an effective and safe training approach for diverse populations.

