## **1. INTRODUCTION**

### **1.1 Background**

Traditional strength training often leads to plateaus, overtraining, and increased injury risk. The BPIT, developed by [name], cycles through five distinct levels of exercise intensity to optimize neuromuscular adaptation, enhance recovery, and minimize biomechanical stress.

- **Line 1:** Ground-Based, Low Intensity
- **Line 2:** Knee-Level, Low-Moderate Intensity
- **Line 3:** Standing, Moderate Intensity
- **Line 4:** Head-Level, Moderate-High Intensity
- **Line 5:** Plyometric/High-Impact, High Intensity

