# 3. RESULTS

### 3.1 Participant Flow and Adherence

- All 23 enrolled participants completed the intervention.
- Mean adherence was 94.9%.

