## 5. CONCLUSIONS

This study provides strong evidence supporting the efficacy and safety of the BPIT 5-Line protocol for improving physical performance and reducing injury risk. The BPIT method is a valuable addition to the strength and conditioning field.

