## 2. Analysis Populations

- Intention-to-Treat (ITT): All 23 enrolled participants
- Per-Protocol (PP): Participants with  $\geq 80\%$  session adherence (actual adherence was 94.9%, so PP  $\approx$  ITT)
- Safety population: All participants who received at least one training session

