#### **4. Injury Incidence**

- Proportion of participants with  $\geq 1$  training-related injury (with 95% Clopper-Pearson exact CI)
- Injury rate per 1,000 training hours

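### The report's safety conclusion rests on one narrow outcome, training-related injury (1 of 23), and goes beyond what the supplied documents plan or report

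*Protocol*

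**What the plan says.** Three places in the Protocol draw a safety conclusion:

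- Executive Summary: "These findings support the BPIT method as an effective and safe training approach for diverse populations".
- Section 4, Discussion: "The low injury incidence rate (4.3%) supports its safety profile".
- Section 5, Conclusions: "This study provides strong evidence supporting the efficacy and safety of the BPIT 5-Line protocol".

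The outcome behind them is narrower. Protocol sections 1.3 and 2.5 make training-related injury a primary outcome. The secondary outcomes in section 2.5 are heart rate variability, heart rate recovery, EMG, knee valgus and spinal curvature, with no adverse-event item. SAP section 1 repeats the injury objective for the six-week period. SAP section 4 plans the "Proportion of participants with $\geq 1$ training-related injury", with a Clopper-Pearson interval, and a rate per 1,000 training hours.

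SAP section 2 defines a set for harm analyses, "Safety population: All participants who received at least one training session", but no later SAP section names it.

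Protocol section 3.2.2 reports one mild muscle strain, 1/23 (4.3%) and 2.54 per 1,000 hours. It does not give the planned interval. Section 4.6 lists the single arm, the small sample and the short duration as limitations, and does not mention how harm was ascertained.

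**The concern.** A statement that a training method is safe covers more than one category of event. Here the evidence is a count of injuries that passed a relatedness judgement. Neither document defines that judgement or says who made it. Nothing is said about other adverse events, injuries judged unrelated, or reasons for absence, so a reader cannot tell whether these were looked for and not found or not looked for.

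The background section itself takes a wider view of harm: "Traditional strength training often leads to plateaus, overtraining, and increased injury risk". Overtraining is not analysed as a harm outcome.

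The limitations already listed do not cover this. A larger, longer, controlled study with the same single harm outcome would have the same gap. A reader who relies on the Executive Summary would take as shown, and for diverse populations, something that rests on one event count in 23 healthy adults.

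**Working it through.** **1. Reproduce the reported figures.**

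Inputs: 1 event and 23 participants (Protocol 3.2.2); three 60-minute sessions a week for six weeks (2.4); "Mean adherence was 94.9"% (3.1).

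- Proportion: 1/23 = 4.35%, reported as 4.3%.
- Planned sessions: 3 × 6 = 18 per participant; 23 × 18 = 414 sessions, or 414 hours.
- Attended sessions: 393/414 = 94.93%, while 392/414 = 94.69% and 394/414 = 95.17%. So 393 is the only whole number that rounds to 94.9%.
- Rate: 1000 × 1/393 = 2.544 per 1,000 hours, reported as 2.54.
- Missed sessions: 414 − 393 = 21. This assumes that every participant had 18 planned sessions.

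The arithmetic in the report holds. The problem is one of scope.

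**2. Supply the interval that SAP section 4 plans.**

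Clopper-Pearson 95% limits for 1/23:

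- Lower: 1 − 0.975^(1/23) = 0.0011, or 0.1%.
- Upper: the p that solves (1 − p)^23 + 23p(1 − p)^22 = 0.025, which is 0.2195, or 21.9%.

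Even for the outcome that was measured, the data are compatible with a true six-week incidence of about one in five.

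**3. Set the claim beside the measurement.**

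| Kind of harm | Planned outcome? | Result given? |
|---|---|---|
| Training-related injury | Yes (Protocol 1.3, 2.5; SAP 1, 4) | Yes, 1/23 |
| Injury from any cause | No | No; 3.2.2 does not say whether the strain was the only injury of any kind |
| Other adverse events | No | No |
| Reasons for the 21 or so missed sessions | No | No |

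The safety wording covers all four rows. The data cover the first.

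**4. Illustrations only.**

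An all-cause figure cannot be computed, because the documents give no such data. To show how much a count of one depends on classification:

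- One more affected participant: 2/23 = 8.7% (exact 95% CI 1.1% to 28.0%).
- Two more: 3/23 = 13.0% (2.8% to 33.6%).

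Nothing in the documents indicates that such cases exist.

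**The case against.** The strongest reply is that this is an overreach of wording and no more. The injury count is right, the design's main weaknesses are admitted in section 4.6, and nothing shows that any harm was left out. Section 3.2.2 can be read as saying that the one strain was the only injury of any kind. Protocol Appendix D also points to a separate protocol file that was not supplied and may describe adverse-event collection. Much of this stands, and it limits the point in several ways.

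- **A reader might infer that the plan prevents other events from being reported.** SAP section 10 lists only Tables 2–5 and Figures 1–4. But injury is in none of those either, and it is planned in SAP section 4 and reported in 3.2.2. The list is therefore not exhaustive.
- **A reader might infer that the relatedness judgement can only lower the count.** It can err both ways: the one strain might itself be unrelated, which would give 0/23. Leaving out unrelated injuries is also how the outcome is defined. The valid point is that relatedness is undefined and no assessor is named.
- **A reader might infer that sessions were missed because of injury.** Nothing links the missed sessions to harm, and no section says that reasons for absence were recorded.
- **A reader might infer that the unused Safety population distorts the result.** All 23 enrolled participants completed, so that set and the ITT set both have 23 members. Naming it would change no number.
- **Overtraining is not wholly ignored.** Resting heart rate and heart rate variability were measured and read as signs of recovery. They were analysed as benefits, however, and not as harm.

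What the reply does not remove is that three places claim safety in general, the supplied documents give one kind of harm, and the limitations do not say so.

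**Conclusion.** The concern holds as a matter of scope. The supplied documents support this statement: one training-related injury was reported in 23 healthy adults over six weeks, 4.3% with an exact 95% CI of 0.1% to 21.9%. They do not support calling the method safe, or claiming strong evidence of safety.

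They equally do not show that the method is unsafe, that any event was concealed, or that other adverse events went uncollected. The finding is only that the report and SAP neither plan nor report them.

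The conclusion assumes that the supplied text is the full account of harm outcomes; the separate protocol file could add to it. The figure of about 21 missed sessions assumes equal planned sessions per participant. The 8.7% and 13.0% are illustrations and carry no weight in the conclusion. The efficacy results are not affected.

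**What to change.** 1. In the Executive Summary, section 4 and section 5 of the Protocol, replace the safety wording with: *one training-related injury (mild muscle strain) was reported in 23 participants over 6 weeks (4.3%, 95% CI 0.1 to 21.9); other adverse events are not reported here*. This wording does not assert that such events were never collected, which the separate protocol file might contradict.
2. In section 4.6, add that harm was ascertained only as training-related injury. State how relatedness was judged and by whom, or that this was not specified.
3. In section 3.2.2, say whether the strain was the only injury of any kind.
4. If other adverse events, all-cause injuries or reasons for the roughly 21 missed sessions (of 414) were recorded, report them next to the training-related count. If they were not, say so. Label any such analysis post hoc: the SAP is dated 30 November 2024, which is also the primary completion date, and its section 10 refers to tables already in the final report.

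The cost is the rewording of three places, a few added sentences and a check of whatever records exist. No new data collection is needed. The downside is a less favourable safety statement and possibly a higher all-cause injury count.
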